### **5.9.1.5 Statistical modelling**

IPTW-weighted Poisson regression model with robust variance estimator (regressed on exposure status in the sample weighted by the IPTW) will be used to estimate adjusted incidence rate ratios and 95% CIs of each outcome.

### **5.9.2 Handling of Missing Data**

Data is dependent on information that was recorded by physicians and nurses into the EHR. It is therefore assumed that the patient did not have the diagnosis of interest if it is not reported in the EHR. No missing data will be imputed. For demographic characteristics, the type of missingness will be evaluated.

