Outcome ascertainment will be performed in two ways. First, data elements within the PEDSnet common data model (CDM), which comprises structured data extracted from EHRs will be examined to identify the select medical events of interest. Each event will be defined using algorithms that will include diagnostic codes and if needed procedure and medication codes, recorded in the EHR. Second, because not all symptoms, signs, and health problems are included in the structured data as diagnosis codes, a chart review of the EHRs for all eligible study patients will be conducted to examine unstructured text data not captured in the CDM to identify additional patients with the select medical events of interest.

Patients with status epilepticus diagnostic codes in their record will be identified from the cohort and will have their results presented separately in sub tables. They will also contribute to the main study populations. This is to fulfill commitment to examine outcomes in SE patients when exposed to lacosamide. It is assumed that any patients treated with a loading dose of LCM will be more likely to be in SE and proving refractory to treatment than the usual seizure presentation in children.

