## **5.5 Variables**

### **5.5.1 Primary outcome measure**

The following primary variables will be measured to meet the study objectives:

- The incidence rate and incidence rate ratio of cardiac disorders (selected preferred terms (PTs) as described in Section 5.5.5)
- The incidence rate and incidence rate ratio of general disorders and administration site conditions (selected PTs as described in Section 5.5.5)
- The incidence rate and incidence rate ratio of injury, poisoning and procedural complications (selected PTs as described in Section 5.5.5)
- The incidence rate and incidence rate ratio of investigations (i.e. the incidence rate of ECG PR prolongation)
- The incidence rate and incidence rate ratio of skin and subcutaneous tissue disorders (selected PTs as described in Section 5.5.5)
- The incidence rate and incidence rate ratio of drug reactions with eosinophilia and systemic symptoms syndrome (selected PTs as described in Section 5.5.5)
- The incidence rate and incidence rate ratio of severe cutaneous adverse reactions (selected PTs as described in Section 5.5.5)
- The incidence rate and incidence rate ratio of hypersensitivity (selected PTs as described in Section 5.5.5)
- The incidence rate and incidence rate ratio of nervous system disorders (selected PTs as described in Section 5.5.5)
- The incidence rate and incidence rate ratio of metabolism and nutrition disorders (selected PTs as described in Section 5.5.5)

- The incidence rate and incidence rate ratio of psychiatric disorders (i.e. abnormal behavior)

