Paraplegic gait (finding)	SCTID: 250035005
On examination - gait spastic (finding)	SCTID: 163685000
On examination - limping gait (finding)	SCTID: 163691003
Investigations	
ECG PR Prolonged	
Electrocardiogram: partial atrioventricular block - long PR (finding)	SCTID: 164902006
Prolonged PR interval (finding)	SCTID: 164947007
Injury, poisoning and procedural complications	
Injection site discomfort	
Injection site burning (disorder)	SCTID: 95389008
Injection site reaction (disorder)	SCTID: 95377006
Injection site disorder (disorder)	SCTID: 95376002

Table 3 SNOMED-CT concepts for the study	
Study outcome	SNOMED code
Injection site dermatitis (disorder)	SCTID: 95393002
Injection site urticaria (disorder)	SCTID: 95394008
Injection site edema (disorder)	SCTID: 95392007
Swelling at injection site (disorder)	SCTID: 213340005
Injection site inflammation (disorder)	SCTID: 95391000
Injection site induration (disorder)	SCTID: 95402002
Induration at injection site (disorder)	SCTID: 213337005
Injection site hypersensitivity (disorder)	SCTID: 95378001
Injection site cyst (disorder)	SCTID: 95396005
Injection site mass (disorder)	SCTID: 95395009
Injection site ulcer (disorder)	SCTID: 95400005
Injection site abscess (disorder)	SCTID: 95382004
Injection site atrophy (disorder)	SCTID: 95404001
Injection site necrosis (disorder)	SCTID: 95397001
Injection site fibrosis (disorder)	SCTID: 95403007
Injection site bruising (disorder)	SCTID: 95401009
Injection site infection (disorder)	SCTID: 95381006
Injection site granuloma (morphologic abnormality)	SCTID: 24389009
Injection site thrombosis (disorder)	SCTID: 95386001
Injection site hemorrhage (disorder)	SCTID: 95385002
Injection site paresthesia (disorder)	SCTID: 95399003
Injection site nerve damage (disorder)	SCTID: 95390004
Injection site malabsorption (disorder)	SCTID: 95387005
Injection site extravasation (disorder)	SCTID: 95384003
On examination - Injection sites abnormal (disorder)	SCTID: 308092004
Injection site sterile abscess (disorder)	SCTID: 95383009
Injection site pigmentation change (disorder)	SCTID: 95380007
Application AND/OR injection site disorder	SCTID: 95363008
Application site rash (disorder)	SCTID: 95371007
Injection site pain (disorder)	SCTID: 95388000
Erythema at injection site (disorder)	SCTID: 213338000
Injection site irritation (disorder)	SCTID: 95379009
Injection site erythema	

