#### 5.9.1.1 Adjustment for baseline characteristics using propensity scores

We will use propensity score and inverse probability of treatment weights (IPTW) to control confounding (Brookhart 2013). The propensity score will be estimated using a logistic regression model, in which higher IV LCM dose (vs. recommended initial/maintenance IV LCM dose) will be regressed on the baseline characteristics. Covariates for inclusion in the propensity score model were selected based on their potential association with the outcomes, including patient characteristics, patient disease history, and treatment history, as indicated on page 35 of the study protocol under section 5.6.6, and on page 21 section 5.6.3 of the protocol, and as listed below:

- Weight
- Sex
- Age at time of seizure treated with loading dose
- Ethnicity (if available)
- PEDSNet site
- Diagnosed medical conditions
- Prior AED/benzodiazepine prescribing (home use) or administration in hospital
- Prior seizure number if available
- Treatment for said seizures (AED and/or benzodiazepine)
- Concomitant prescribing
- Pre-existing medical conditions of interest for the safety evaluation: cardiac conditions, dermatologic conditions, vascular conditions, injury, poisoning and procedural complications, general disorders and administration site conditions, investigations, drug reaction with eosinophilia and systemic symptoms syndrome, severe cutaneous adverse reactions, hypersensitivity events
- Prior EEG data at last seizure

After the propensity scores have been generated, we will assess for violations of underlying assumptions. Positivity violations will be assessed by plotting the propensity score distributions in an overlay plot for the comparator groups. To evaluate adequate overlap of the propensity scores, we will visually inspect the density distribution of the propensity scores (Rosenbaum and Rubin, 1984). The performance of the model will be evaluated by assessing the covariate balance across the treatment groups. Standardized differences will be used to compare the mean or prevalence of baseline covariates between the comparator treatment groups in the samples

weighted by the inverse probability of treatment. Additionally, continuous variables will be compared using graphical methods including boxplots and nonparametric density plots.

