### **5.9.1.2 Analysis of primary and secondary outcome measures**

Only the first occurrence of the event after the index date will be counted in analyses. For both the IV LCM group and comparator group, counts and frequency of events will be recorded. For both the IV LCM high dose group and comparator group, several incidence rates will be calculated. First, the overall incidence rate of any event of interest will be calculated. Second, incidence rates for each of the following events will be calculated individually: Cardiac disorders, Skin and subcutaneous tissue disorders, Nervous system disorders, Metabolism and nutrition disorders, Psychiatric disorders, Injury, poisoning and procedural complications, General disorders and administration site conditions, and Investigations, Drug reaction with eosinophilia and systemic symptoms syndrome, Severe cutaneous adverse reactions and Hypersensitivity events. Third, incidence rates for each subcategory of the abovementioned events and associated 95% confidence intervals will be calculated. The incidence rate of each event with associated 95% confidence interval will be calculated for the IV LCM high dose group and comparator group.

The numerator will be the total number of patients with the outcomes identified during the follow-up period. The denominator will be in patient-days. That is, the total summation of individual patient-days at risk up to the first occurrence of the AE of interest for subjects with

that AE, and the total patient-days at risk calculated up to the censoring date i.e. discontinuation of IV LCM plus 30 days or loss to follow-up for those subjects not experiencing that AE. Incidence rates will be presented with a 95% exact confidence interval based upon the Poisson distribution or another relevant model if there is nonconvergence. It is important to note incidence rates per time at risk are based on a constancy assumption. That is, the rates per unit of time assume that the event occurs with a constant rate over time. Events that are more likely to occur early or late relative to the initial exposure or with an increasing or decreasing hazard rate over time would not meet the constancy assumption and these rates should be viewed with caution. The person time for each patient will be calculated as the total number of days of follow-up as described in Section 5.3.3 .

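### PR prolongation needs an ECG to be found, but children with no ECG count as event-free, so unequal ECG use between dose groups can shift its rate ratio

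*Protocol*

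**What the plan says.** - **Outcome.** Section 5.5.1 lists as a primary measure "The incidence rate and incidence rate ratio of investigations (i.e. the incidence rate of ECG PR prolongation"). Table 3 in section 5.5.5 defines it by two codes: "Electrocardiogram: partial atrioventricular block - long PR (finding") and a prolonged-PR-interval finding.
- **Unrecorded outcomes.** Section 5.9.2: "It is therefore assumed that the patient did not have the diagnosis of interest if it is not reported in the EHR". It adds: "No missing data will be imputed".
- **Denominator.** Section 5.9.1.2: "The denominator will be in patient-days". A child without the event contributes all days up to censoring, and having had an ECG is not a condition.
- **Comparison.** Section 5.9.1.5 uses an "IPTW-weighted Poisson regression model with robust variance estimator (regressed on exposure status in the sample weighted by the IPTW").
- **Adjustment.** The propensity covariates in section 5.9.1.1 include diagnosed conditions, prior and in-hospital antiepileptic or benzodiazepine treatment, site and pre-existing cardiac conditions. The only test named is an EEG: "Prior EEG data at last seizure". ECG use is not listed, and neither is ICU location.
- **Expected difference between groups.** Section 5.1 states this assumption: "any patients treated with a loading dose of LCM will be more likely to be in SE and proving refractory to treatment". The comparison made there is with ordinary paediatric seizures.

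**The concern.** This is retrospective routine care, and neither inclusion nor exclusion criteria (5.2.1, 5.2.2) mention an ECG. A child with no ECG cannot have either Table 3 code, so the 5.9.2 rule turns not tested into no event. Two things are at stake.

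1. Estimating incidence is the stated primary objective, and the all-patient figure would be too low in both groups.
2. If one dose group had ECGs more often after the index dose, its recorded rate would be higher for that reason alone. On the protocol's own expectation about loading-dose children, closer monitoring of that group is plausible, though the protocol does not say so. The reader would then be unable to tell a conduction signal from a detection difference.

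**Working it through.** **Nothing to reproduce.** The protocol has no event or power calculation for this outcome. Section 5.9.3 gives only a feasibility count of 875 children before the full criteria, with no split by dose group. It gives no ECG frequency and no PR-prolongation risk, so those inputs below are assumptions.

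**Formula.** Let p be the risk of PR prolongation, and e the weighted share of a group with a post-index ECG. Assume that within a group testing is unrelated to PR status. Then:

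- recorded risk = p × e
- observed ratio = (p_H × e_H) / (p_R × e_R) = true ratio × (e_H / e_R)

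**Numbers, with p = 10% in both groups (no dose effect):**

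| ECG share, high vs recommended | Recorded risk | Observed ratio |
|---|---|---|
| 50% vs 50% | 5% vs 5% | 1.00 |
| 50% vs 40% | 5% vs 4% | 1.25 |
| 60% vs 40% | 6% vs 4% | 1.50 |
| 40% vs 60% | 4% vs 6% | 0.67 |

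In the last row a true ratio of 1.5 would be seen as 1.5 × 0.40/0.60 = 1.0. In every row the assumed 10% is recorded as 4% to 6%.

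**Patient-day version.** With constant hazard λ over T days, and untested children contributing full time:

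rate(e) = e(1 − exp(−λT)) / [e(1 − exp(−λT))/λ + (1 − e)T]

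For λ = 0.002 or 0.01 per day and T = 7 or 37 days, 60% vs 40% gives ratios of 1.50 to 1.55. The simple formula therefore carries over to the planned rate ratio. Limiting both events and patient-days to tested children gives 1.00, under the same assumption about testing.

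**Chance of a spurious significant result.** This uses a two-sided 5% comparison of two proportions, an assumed 1:1 split, 60% vs 40% tested and no dose effect:

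| Total children | p = 5% | p = 10% |
|---|---|---|
| 875 | 16% | 27% |
| 400 (assumed after criteria) | 9% | 15% |

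**Does the plan address post-index testing elsewhere?**

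- The outcome-definition sensitivity analysis in 5.9.1.4 adds a later medication or procedure code to a diagnosis record. It starts from detected cases.
- Chart review (5.4.1) cannot recover a PR interval that was never measured.
- The 5.9.4 argument for balanced recording concerns history and prescriptions before the index date. Its misclassification paragraph concerns algorithms and completeness of notes, not whether a test was done.

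**The case against.** The strongest reply is that the plan already handles much of the imbalance. Refractory status epilepticus, the reason given for expecting unequal monitoring, is largely a baseline feature. The propensity covariates on diagnoses, prior treatment, site and cardiac history will capture part of it. Children with status epilepticus get separate tables (5.1, 5.9.1.2), and section 5.9 stratifies by indication and by ICU or other department. This stands: a reader might infer that weighting leaves the whole testing difference in the ratio, and the documents do not support that. Only the remainder matters, and the shares in the working are therefore weighted shares. The safeguards are still proxies for ECG use, and the Executive Summary makes the indication and ICU strata conditional on numbers.

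A reader might also infer that the rate ratio reflects ECG use as much as drug effect, or that the bias must inflate the high-dose rate. Neither follows. Without ECG frequencies no size or direction can be read from the protocol, and with equal ECG use the ratio is unbiased under the working's testing assumption. If clinicians tested the children most at risk, the understatement of incidence is also smaller than shown.

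Finally, case definitions are still to be developed (5.5.5), and a tested-subset analysis could sit in a statistical analysis plan that is not shown. That is fair for the subset analysis. It does not reach the 5.9.2 rule, which the protocol itself fixes without exception.

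**Conclusion.** The point holds as a detection problem of unknown size and direction. For ECG PR prolongation, and in the same way for first-degree AV block, the all-patient incidence is likely understated in both groups. The rate ratio is multiplied by whatever ratio of post-index ECG use remains after weighting and within the planned strata. The illustrated factors of 1.25, 1.5 and 0.67 rest on assumed ECG shares and on testing being unrelated to PR status within a group. They show how the bias works and are not estimates for this study. The plan as written would not show whether ECG use differed. The improvement is cheap and should be made.

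**What to change.** 1. **Report testing.** Identify ECGs during the 5.3.3 follow-up from procedure codes, which Table 4 shows are in the common data model. Give the crude and weighted share of children with at least one, by dose group.
2. **Keep the all-patient rate and rate ratio, and relabel them** as the rate of recorded PR prolongation (and of recorded first-degree AV block). Add a sensitivity analysis giving the rate and rate ratio among children with a post-index ECG, with events and patient-days both limited to those children. State whether days before the first such ECG count. Note that the subset is selected by clinicians and conditions on a post-index variable.
3. **Reword the text.** In 5.9.2, say that for these ECG-dependent outcomes no record in a child without a post-index ECG means not assessed, so the all-patient rate is a rate of detected events. Add unequal detection to the limitations in 5.9.4.

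The cost is one procedure-code query, a few table rows and some protocol wording. The tested subset is smaller and selected, which is why it belongs beside the all-patient result and does not replace it.

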### 5.9.3 Sample size

To date, the feasibility assessment included the total number of subjects between 1 month to 17 years who had at least one IV administration of LCM, which totaled 875 patients. To obtain count data on the two comparator groups i.e. loading dose or initial maintenance dose, requires complex programming to evaluate dose data, patient weight, age and so forth. Some of these data may be available in structured fields, but there might be need for additional information from the medical charts to calculate accurate dose information. As this protocol will be finalized post full review by the Division, at which time programming will commence, the feasibility analysis to date was thus limited to population count.

We acknowledge that the total population number will be reduced post application of the full study criteria but should nevertheless still retain several hundred patients, enough to allow adequate and accurate evaluation of safety data for LCM in this specific population.

### 5.9.4 Strength and Limitations

**Unmeasured confounding:** As the study is comparing the incidence rates of select medical events in patients who are treated with a high dose of IV lacosamide to patients who are treated with recommended dose of IV lacosamide, the major confounders are factors that impact the incidence rate of these medical events of interest. These factors include age, gender, comorbidities, and exposure to other medications which are measured. Unmeasured confounding would only occur if there was a major confounder which is not measured and thus missed from the adjusted model. However, the electronic medical records include demographic information, the medical history of the patients and any medications prescribed by the physicians. Therefore we anticipate that information on most of the confounders will be available. It is possible that there will be missing information on some comorbidities, if they are not recorded by the physicians and on medications that are either bought over counter or prescribed outside the PEDSnet healthcare network. Nevertheless, most hospitals in the PEDSNet healthcare network are large with epilepsy comprehensive care centers within the neurology departments, so we anticipate reliable background medical. We do not anticipate that there will be a disproportionate difference in the recording of the medical history data and prescription of medications in patients who are treated with high dose lacosamide and recommended lacosamide prior to the index date. Therefore, we anticipate that there will be minimal unmeasured confounding. Additionally, the analysis will be using new user design to minimize confounding by indication.

**Reduced generalizability:** The PEDSnet database is restricted to subjects seeking and receiving medical care within a facility affiliated with PEDSnet. Data is obtained from multiple care sites and type (e.g. in-patient, out-patient, emergency department). However, if a report of an event was made or a subject was treated for an event at a facility that is not affiliated PEDSnet, this information will not be captured in the PEDSnet data. However, as most events are anticipated to occur within 24 hours of receiving IV LCM, the impact of this is likely to be low.

**Misclassification:** Ascertainment of outcomes will be made using controlled vocabularies. Currently there are no validated algorithms for defining these outcomes in EHR data therefore there is a risk for misclassification. Misclassification will be minimized through chart reviews that will be conducted by experienced healthcare personnel. Additionally, sensitivity analyses will be conducted to assess the impact of the case definitions on the effect estimates. Information available from outpatient or ER reports is likely not to provide as complete information as that recorded during hospitalisation, however, despite this it is likely that any severe AEs will be recorded. As noted, available data from the chart review is expected to be

complete for patients in an inpatient setting. In particular nurses notes should comprise detailed information on patient responses and patient reported outcomes. As IV LCM is generally administered in an inpatient setting, we therefore expect recording of immediate AEs to be well documented, including those that may be less severe such as injection site irritation/pain.

**Strengths:** Despite these limitations, this assessment will provide a large sample pediatric of patients exposed to off-label IV LCM, facilitating timely characterization of the safety profile of these patients and informing the pediatric trial program.

## **6 PROTECTION OF HUMAN SUBJECTS**

### **6.1 Patient consent for data usage and processing**

The data will be completely anonymized and thus will not contain any identifiable patient data (eg, patient initials or date of birth). In accordance with the "International Ethical Guidelines for Epidemiological Studies" [Prepared by the Council for International Organizations of Medical Sciences (CIOMS) in collaboration with the World Health Organization (WHO), 113 pp., Geneva: 2008, pp 21] - cit. "records and specimens taken in the course of clinical care, or for an earlier study, may be used for research without the consent of the patients/subjects only if an ethical review committee has determined that the research poses minimal risk, that the rights or interests of the patients will not be violated, that their privacy and confidentiality or anonymity are assured, and that the research is designed to answer an important question and would be impracticable if the requirement for informed consent were to be imposed" - it is considered for this study that a data collection patient informed consent form is not required as the patients are unidentifiable.

